Title: Study 2 Learning New Words from Overhearing in Children with Autism Spectrum Disorder (ASD)

NCT Number: NCT05192109

Document date: 12/24/2024

The objective of this study was to see whether autistic and non-autistic children learn new words when they are presented via videoconferencing in one of two conditions: as part of speech directly addressed to the child (Addressed condition), as part of speech they overhear (Overheard condition). Children participated in the experimental task in both conditions (within-subject design). The method was a behavioral experiment in which children were exposed to a novel word (e.g., “toma”) in the context of one of three objects. The exposure either occurred with the experimenter looking directly at the child through the webcam (Addressed condition) or looking at another adult (Overheard condition). They were then shown the three objects and given a prompt to identify which object is labeled by the novel word (e.g., “where is the toma?”). Children’s eye gaze was coded as a measure of which object they preferred to look at after the prompt. After a delay of a few minutes, the test was repeated as a measure of retention.

The primary dependent variable reported here is the proportion of time children spend looking at the target object in each condition for each of the first test and the retention test. Track loss data points (that is, data points on which the child’s gaze could not be ascertained) are removed from analysis.

For each of the first test and the retention test, the primary statistical analysis involves asking whether children’s preference to look at the target is significantly greater in one condition than the other, and/or for one group or the other. Mixed-effects regression analyses are used with the proportion—empirical-logit transformed—of target looking as the dependent measure, participant as random effect, and condition and group and their interaction as fixed effects. If the interaction is significant, post-hoc testing using estimated marginal means is used.

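### Does leaving the denominator of the looking proportion unstated mean that the primary outcome mixes attention with object preference?

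*Combined protocol and SAP*

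**What the plan says.** The document is a short combined text without section numbers. Three of its statements bear on this point.

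- **Method (first paragraph).** At test, "They were then shown the three objects and given a prompt to identify which object is labeled by the novel word". The child's "eye gaze was coded as a measure of which object they preferred to look at after the prompt".
- **Outcome (second paragraph).** "The primary dependent variable reported here is the proportion of time children spend looking at the target object in each condition", for the first test and for the retention test. On exclusions, the sentence defining track loss ends "gaze could not be ascertained) are removed from analysis".
- **Analysis (third paragraph).** The question is whether "preference to look at the target is significantly greater in one condition than the other", or greater in one group than the other. The proportion is empirical-logit transformed and modelled with "participant as random effect, and condition and group and their interaction as fixed effects".

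The text does not list the gaze codes, write out the denominator, or say what happens to a look that was seen clearly but fell on none of the three objects.

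**The concern.** A proportion needs a denominator, and two are possible here: all data points with a known gaze direction, or only the points on one of the three objects. A child plainly looking at a parent or the ceiling has an ascertained gaze, so the track-loss definition, taken strictly, does not remove that point. If nothing else removes it, it counts as time off the target. The outcome then equals object preference multiplied by the share of time spent on the objects.

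That would matter in this design. Autistic and non-autistic children are compared over videoconference, and the conditions differ in whether the experimenter looks at the child or at another adult. Attention to the screen could plausibly vary with either factor. The model has no term for attention, and a random participant effect does not remove a systematic difference between groups. A difference in attention could then be read as a difference in word learning.

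**Working it through.** **Figures in the plan.** The document gives no sample size, effect size, preference level or off-object rate, so there is no stated figure to reproduce. Every value of q and a below is an assumption.

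**Set-up.** Let q be the share of on-object time spent on the target, and a the share of ascertained time spent off all three objects.

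- Denominator A (all ascertained points): outcome = q(1 − a).
- Denominator B (objects only): outcome = q(1 − a)/(1 − a) = q.

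**Equal preference, unequal attention.** With q = 0.50 in both cells and a = 10% in the first:

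| Second cell a | A, first cell | A, second cell | Logit difference under A | Under B |
|---|---|---|---|---|
| 15% | 0.50 × 0.90 = 0.45 | 0.50 × 0.85 = 0.425 | −0.201 − (−0.302) ≈ 0.10 | 0 |
| 20% | 0.45 | 0.50 × 0.80 = 0.40 | −0.201 − (−0.405) ≈ 0.20 | 0 |
| 30% | 0.45 | 0.50 × 0.70 = 0.35 | −0.201 − (−0.619) ≈ 0.42 | 0 |

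The empirical logit, ln[(y + 0.5)/(n − y + 0.5)] with an assumed n = 100 ascertained points, gives nearly the same: ln(45.5/55.5) − ln(40.5/60.5) = 0.20 and ln(45.5/55.5) − ln(35.5/65.5) = 0.41. For 10% against 30%, the empirical-logit difference is 0.34 at q = 1/3 and 0.48 at q = 0.60. Under B it stays within 0.003 of zero in every case tried.

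**Which contrasts are exposed.**

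- Equal off-object shares in the cells compared: difference 0 under A. Only the level falls; three-object chance drops from 0.333 to 0.300 at a = 10%. The primary analysis compares conditions and groups, not looking against chance, so this does not affect it.
- A gap between groups only, with equal preference: the group effect is exposed; the condition and interaction effects are not.
- A gap between conditions: the condition effect is exposed.
- A condition gap that differs by group: the interaction is exposed. With q = 0.50 throughout, a = 10%/15% in one group and 10%/30% in the other, the spurious interaction under A is 0.31 on the empirical-logit scale; under B it is 0.

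**Rejection rates.** Simulations with equal preference of 0.50, 20 to 50 children per group, 90 data points per condition and clustered gaze, using t-tests in place of the mixed model, rejected the group effect under A in 6–9% of runs (10% v 15%), 10–22% (10% v 20%) and 23–67% (10% v 30%). Under B the rate was 4–6%. These figures cannot be carried over to the trial. At 30 per group, with no between-child variation and 10% v 30%, the rate under A was 30% at preference 1/3, 46% at 0.50 and 78% at 0.75, so it moves widely with one assumed input.

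**Which denominator the text supports.**

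- For A: the track-loss definition covers only gaze that could not be determined, and no other exclusion is named.
- For B: the method paragraph describes the measure as which object the child preferred, and the analysis paragraph asks about preference for the target. Both describe a choice among the displayed objects.
- For neither: the plan does not say that track loss is the sole exclusion, and it mentions no off-object code that is kept as non-target time.

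Reading A therefore rests on an inference from silence. Reading B follows the stated purpose of the measure, although the text does not settle it.

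**The case for a change.** The strongest case for a change is that two careful analysts could follow this text and compute different primary outcomes. Nothing elsewhere in the document fills the gap. Group is one of the stated primary comparisons, and it is the contrast most open to a difference in attention between autistic and non-autistic children. One or two sentences would settle the point at almost no cost, and off-object and track-loss shares by group and condition would let a reader judge it directly.

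Most of that stands as description: the denominator is unstated, the model cannot separate attention from preference, and a sentence of definition would help readers. It does not show that any rule in the plan gives a wrong result. To claim that the plan literally keeps off-object looks, one must add the word only to the exclusion sentence, and the plan does not contain it. The larger simulated rates need an assumed gap of 20 percentage points in off-object looking, and the document has no attention data to support a gap of any size. If objects-only was already the rule, nothing would be recomputed and no result would move.

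**Conclusion.** No change to the plan follows. The document omits a definition, and analysts who set out to measure which of three objects a child prefers would probably supply the objects-only denominator. The conditional arithmetic is correct: at an assumed preference of 0.50, off-object shares of 10% against 20% or 30% would give spurious logit differences of 0.20 or 0.42. Harm, however, needs two facts that the document does not give: that ascertained off-object looks were kept, and that their share differed between the groups or conditions compared. If either is absent, a group or condition difference at equal preference is 0. The size of any bias in this trial therefore cannot be stated.

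This conclusion rests on reading the measure as a preference among objects, which the wording favours but does not prove. It would need to be revisited if off-object looks turned out to have been counted as non-target time.

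### The objective asks whether each group learns new words in each condition, but every test described is a comparison between conditions or groups and none is against a no-learning level

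*Combined protocol and SAP*

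**What the plan says.** The document is a three-paragraph summary without numbered sections.

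- **Objective (first paragraph):** to see "whether autistic and non-autistic children learn new words when they are presented via videoconferencing in one of two conditions", the two being Addressed and Overheard. Each child takes part in both, so there are 2 groups × 2 conditions = 4 cells.
- **Method (first paragraph):** the word is presented "in the context of one of three objects", all three objects are then shown, and "eye gaze was coded as a measure of which object they preferred to look at after the prompt". The second assessment is described as follows: "After a delay of a few minutes, the test was repeated as a measure of retention".
- **Primary dependent variable (second paragraph):** "the proportion of time children spend looking at the target object in each condition for each of the first test and the retention test". Points where gaze tracking was lost are removed. Whether looks away from all three objects stay in the denominator is not stated.
- **Primary analysis (third paragraph):** at each test, the question is whether "preference to look at the target is significantly greater in one condition than the other, and/or for one group or the other". The model is a mixed-effects regression on the empirical logit with a participant random effect and "condition and group and their interaction as fixed effects". The only further step is conditional: "If the interaction is significant, post-hoc testing using estimated marginal means is used".

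No chance level, baseline looking period, control word, or test of an intercept or cell mean is mentioned.

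**The concern.** Whether children learn a word is a question about the level of target looking in a cell. Whether they learn it better in one condition or group is a question about differences between cells. The objective is worded as the first and the tests described address only the second.

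Two misreadings follow. If no contrast is significant, the result fits all cells having learned and no cell having learned, which are opposite answers to the objective. If Addressed exceeds Overheard, the result fits overheard words being learned less well and overheard words not being learned at all. The study title is about learning from overhearing, so the Overheard cells matter most, and the described tests leave them unresolved.

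**Working it through.** The document states no sample size, SD, alpha, effect size or power, so there is no figure to reproduce. The point is first structural; the numbers only illustrate it.

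**1. Algebra.** Write the model mean as α + β·condition + γ·group + δ·condition×group. Adding a constant to all four cells changes α only. The tests described concern β, γ and δ.

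**2. Mixed-model check.** Assumed: 30 children per group, between-child SD 0.5 and residual SD 0.6 on the logit scale, one observation per child per cell. The same residuals were used while all cells moved together.

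| All cells at | Condition | Group | Interaction | Intercept | Cell t against logit(1/3) |
|---|---|---|---|---|---|
| 1/3 | 0.059 (p=0.70) | −0.033 (p=0.85) | 0.026 (p=0.91) | −0.788 | −0.90 to −0.35 |
| 0.45 | same | same | same | −0.296 | 2.42 to 4.41 |
| 0.60 | same | same | same | 0.310 | 6.45 to 10.28 |

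With no interaction, the estimated-marginal-means step is never reached.

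**3. A positive condition effect.** With logit(p) = ln[p/(1−p)]:

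- logit(0.50) − logit(1/3) = 0 + 0.693 = 0.693
- logit(0.6207) − logit(0.45) = 0.492 + 0.201 = 0.693

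The same contrast arises with Overheard at 1/3 and with Overheard at 0.45.

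**4. Simulation on the proportion scale.** Assumed: beta-binomial target share, 60 usable frames, one trial per cell, 30 children per group, child-level SD 0.18, within-child correlation 0.5. Cell tests are against 1/3, Holm-adjusted over four cells.

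| True shares | Planned tests | Cell tests |
|---|---|---|
| All cells 1/3 | nothing significant in 86% of runs | any cell called learned in 1.7% |
| All cells 0.60 | nothing significant in 86% | each cell called learned in 100% |
| Addressed 0.50, Overheard 1/3 | condition effect 0.84 logits, significant in 100% | each Overheard cell called learned in about 1% |
| Addressed 0.62, Overheard 0.45 | condition effect 0.82 logits, significant in 100% | about 90% (53% at SD 0.27) |

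The 86% is simply the chance that three nearly independent null tests all miss: 0.95³ = 0.857. It hardly depends on sample size or SD (0.848 to 0.865 over 20 to 40 per group and SDs of 0.10, 0.18 and 0.27). The fitted effects exceed 0.693 because logits are averaged over children who vary.

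**5. Power of one cell test, by hand.** True share 0.45, n = 30, SD 0.18:

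- Total SD = √[0.18² + (0.45×0.55 − 0.18²)/60] = 0.190; SE = 0.190/√30 = 0.0346.
- (0.45 − 0.333)/0.0346 = 3.37.
- At 0.05 (critical t 2.045): Φ(3.37 − 2.045) ≈ 0.91. At 0.05/4 = 0.0125 (critical t 2.663): Φ(3.37 − 2.663) ≈ 0.76.

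The simulation gives 0.910 and 0.760.

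**6. How far 1/3 can be trusted.** If exposure alone lifts target looking to 0.40 without learning, the test against 1/3 at 0.05 wrongly indicates learning in 45% of runs (SD 0.18; 86% at SD 0.10, 23% at SD 0.27). Post-prompt minus pre-prompt share, with the same salience before and after, gives 2.3% to 2.7%. The denominator matters too: if 10% to 40% of retained looking is off all three objects, the no-learning share falls to 0.90/3 = 0.30 down to 0.60/3 = 0.20. A default test of a cell against zero on the logit scale would test 0.50, which is none of these.

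**The case against.** Four points can be made for the plan.

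- **The objective can be read as comparative.** The third paragraph frames the primary question that way, and the planned model suits it. This stands for the comparative question, but the objective's verb is to learn, not to learn better.
- **The summary is short and not exhaustive.** It says what the primary analysis involves, so a cell test may have been done without being described. That limits the conclusion to what is described.
- **Only the test results coincide, not all the output.** Reported target-looking proportions would show roughly 0.33 or roughly 0.60, and the fitted intercept moves. This is correct. What is missing is inference on those levels; the document promises neither values by group within condition nor intervals. Estimated marginal means could be set against a constant, but none is named and the step waits on the interaction.
- **The obvious reference may not measure learning.** The target was singled out during exposure, so looking above 1/3 may reflect salience. This is the strongest objection, and the false-positive rates above bear it out. The clean separation in the step 4 table holds only without salience. The objection limits what a test against 1/3 can claim; it does not make the contrasts answer the objective.

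**Conclusion.** The concern holds. As described, the analysis does not test whether any group learned in either condition, which is what the objective asks. This follows from the form of the model and needs no assumption about sample size or variance. The size of the ambiguity is illustrated only under assumed inputs: the planned tests behave alike (86% against 86% with nothing significant; 100% against 100% with a condition effect) in situations whose answers to the objective differ. The planned contrasts remain valid for comparing conditions and groups, so this should be fixed but does not undermine them. Confidence is high that the gap exists. How well any cell test measures learning depends on the reference, and the document does not give enough to settle that.

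**What to change.** Keep the planned contrasts. At each of the first and retention tests, whatever the interaction p-value:

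1. Report the four group-by-condition estimates with 95% CIs, on the proportion scale used for the cell tests.
2. For each child, take the target share of time on the three objects, averaged over that child's trials in the cell, with off-object looks excluded. Test it against 1/3, Holm-adjusted over the four cells. State that the first and retention tests are separate families, and say so if the planned model uses a different denominator.
3. State that 1/3 means no learning only if the objects are equally attractive without learning. Counterbalanced target identity, if used, covers the objects' own appeal but not attention drawn by the exposure. If pre-prompt looking was recorded, use post-prompt minus pre-prompt share against 0 instead.
4. Report a non-significant cell as learning not shown, and use its CI to say how much is ruled out.
5. Label these tests as added if data have already been seen.

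**Cost.** A little more analysis and no new participants. Unadjusted, four independent cell tests at 0.05 carry a family-wise error of 1 − 0.95⁴ = 0.185, and eight carry 0.337, so adjustment is needed. At 30 per group and a true share of 0.45, power per cell falls from 0.91 unadjusted to 0.76 at Holm's first step (SD 0.27: 0.61 to 0.36). Under full Holm it is 0.87 if all four cells are at 0.45. One family of eight would give 0.66 at its first step (0.05/8 = 0.00625). The pre-prompt reference guards against salience but has power of only 0.41 to 0.70 at 0.0125, for pre-post correlations of 0 to 0.5.

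### Does the plan need an alpha level and a multiplicity rule for its four primary questions?

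*Combined protocol and SAP*

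**What the plan says.** The combined protocol and SAP is three unnumbered paragraphs. The second makes primary "the proportion of time children spend looking at the target object in each condition for each of the first test and the retention test", so both occasions carry that label. The third asks, for each occasion, whether looking at the target is "significantly greater in one condition than the other, and/or for one group or the other". The model has "participant as random effect, and condition and group and their interaction as fixed effects". The only conditional step is this: "If the interaction is significant, post-hoc testing using estimated marginal means is used". That rule governs follow-up contrasts and does not rank or protect the condition and group questions. No paragraph states an alpha, whether tests are one- or two-sided, a testing order or a multiplicity policy. Equally, none claims an overall 5% error rate or defines success as any one positive result.

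**The concern.** Two questions on two occasions make four primary tests. The word joining condition and group could be taken to mean that significance on either will do. With no alpha or order given, a reader who meets one significant result, say the group difference at retention with p = 0.03, cannot tell whether to read it as a finding in its own right or as the best of four attempts. In a trial with one joint claim, that gap would matter: the claim could rest on whichever test came out, with an error rate well above the nominal level. The interaction is also tested on each occasion, which would bring the count to six.

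**Working it through.** The plan states no sample size, power, alpha or error rate, so it has no figure to reproduce. The check asks how large the joint error could be.

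Inputs from the plan:

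- Two occasions, both primary (second paragraph).
- Two questions per occasion, condition and group (third paragraph), so 2 × 2 = 4 tests.
- The same children on both occasions: "After a delay of a few minutes, the test was repeated as a measure of retention". A positive correlation between occasions is therefore likely, but no value is given.
- Condition varies within child (first paragraph), and group varies between children.

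Assumptions:

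- Two-sided 0.05 per test.
- Condition and group statistics independent, which needs balanced data and sum-coded effects.
- The same correlation r between occasions for both effects, taken over its range from 0 to 1.

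Let p(r) be the probability that at least one of two two-sided 0.05 tests rejects under the null, from the bivariate normal distribution with correlation r. The joint rate is 1 − (1 − p)² for four tests and 1 − (1 − p)³ for six.

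| r | p(r) | Four tests | Six tests |
|---|---|---|---|
| 0 | 0.0975 | 18.5% | 26.5% |
| 0.3 | 0.0951 | 18.1% | 25.9% |
| 0.5 | 0.0907 | 17.3% | 24.8% |
| 0.7 | 0.0835 | 16.0% | 23.0% |
| 0.8 | 0.0781 | 15.0% | 21.6% |
| 0.9 | 0.0704 | 13.6% | 19.7% |
| 1 | 0.0500 | 9.8% | 14.3% |

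Example at r = 0.7: 1 − (1 − 0.0835)² = 0.160.

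The independence assumption matters little. Suppose the model used reference coding in equal groups. The condition and group terms would then be simple effects correlated at √(1 − w)/2, where w is the within-child correlation between conditions. For w between 0.5 and 0 this is 0.35 to 0.5. The four-test rate becomes about 17.3% to 18.0% at r = 0, 12.6% to 13.1% at r = 0.9 and 9.1% to 9.4% at r = 1. So 9.8% is not a strict floor, but the picture is the same.

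Next, the price of adjusting. The first Holm threshold for four tests is 0.05/4 = 0.0125, with critical value 2.498 in place of 1.960.

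- 80% power at 0.05 means an expected statistic of 1.960 + 0.842 = 2.802. At 0.0125 the power is Φ(2.802 − 2.498) = 62%.
- 90% power means 1.960 + 1.282 = 3.242, and the power becomes Φ(3.242 − 2.498) = 77%.

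Last, which results are affected. In a family of four, any p-value below 0.0125 survives Holm. Values from 0.0125 to 0.05 may or may not survive, depending on the other three. In a family of six the first threshold is 0.05/6 = 0.0083.

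**The case for a change.** The strongest case for a change is that the four tests bear on one objective, learning words from addressed versus overheard speech in autistic and non-autistic children. The joint rate exceeds 5% at every correlation in the table, and a sentence stating the intent, with a column of Holm-adjusted p-values, would cost almost nothing and remove no result. The facts behind this stand: the text is silent, and the arithmetic is right.

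The step to a needed change does not stand. A familywise rate measures the risk attached to a single claim that something among the four is positive, and the plan makes no such claim. Whether children look more at the target in one condition, whether the groups differ, and whether either effect holds after a delay are different scientific questions, each with its own answer. The linking word in the third paragraph can just as well list the questions as define a success rule. Even the size of the family, four or six, is a matter of reading.

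Timing also weakens the remedy. The study description is in the past tense, so an alpha or a Holm family written in now could not be presented as pre-specified. Adjusted p-values can still be shown beside the unadjusted ones with that label. Any reader given the four p-values can work them out.

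**Conclusion.** The observation is accurate, but it does not identify an error. Under the global null, with two-sided 0.05 per test and independent condition and group statistics, the chance of at least one false positive among four tests is about 10% to 18.5%, depending on an unstated correlation. Neither end of that range has better support from the plan, though retesting the same children within minutes makes a correlation of 0 unlikely. Counting the interaction raises the range to about 14% to 26.5%. These are worst-case joint rates, and each question taken separately keeps the assumed 5%.

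The missing alpha is a detail that analysts would ordinarily fill with 0.05. Whether to adjust across distinct questions is a trade-off on which experienced statisticians differ: adjustment gives joint control that the plan never claimed and lowers 80% power for an isolated effect to about 62%. No change to the plan follows. The conclusion would differ if the results were presented as one joint claim resting on any single positive test.

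### Does the primary mixed model need weights because track loss leaves unequal numbers of valid gaze points?

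*Combined protocol and SAP*

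**What the plan says.** The Combined protocol and SAP is a single page without section numbers. Its second paragraph defines the outcome: "The primary dependent variable reported here is the proportion of time children spend looking at the target object in each condition", separately for the immediate and the retention test. It then deals with lost gaze: "Track loss data points (that is, data points on which the child’s gaze could not be ascertained) are removed from analysis".

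The third paragraph gives the model, a mixed-effects regression on the empirical logit of the proportion "of target looking as the dependent measure, participant as random effect, and condition and group and their interaction as fixed effects". Condition is compared within child: "Children participated in the experimental task in both conditions (within-subject design".

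The page mentions no weights, no count-based likelihood and no minimum of valid gaze points. It does not say that the model is unweighted; it is silent. It also gives no sample size, alpha, number of trials, window length, sampling rate or track-loss rate.

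**The concern.** Once lost points are dropped, each proportion rests on its own number N of valid points, which can differ by child, condition and test. The precision of an empirical logit depends on N, and so does its value at the extremes: a child who looks only at the target scores higher with a long record than with a short one.

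A linear mixed model fitted without weights treats all these values as equally informative. A child with a handful of usable points would then count as much as one with a complete record, which could cost power for condition, group and interaction. If autistic and non-autistic children differ in track loss, residual variance could also differ by group, against the model's common-variance assumption. Weighting by valid points looks like a cheap cure.

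**Working it through.** The plan states no power or sample-size figure, so there is nothing to reproduce. The question is whether the inequality matters, and whether weighting reliably helps.

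**1. The transform.** With y points on target out of N, the empirical logit is ln((y + 0.5)/(N − y + 0.5)). At 100% on target (N values illustrative):

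- N = 150: ln(150.5/0.5) = 5.71
- N = 30: ln(30.5/0.5) = 4.11
- N = 5: ln(5.5/0.5) = 2.40

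If gaze points were independent, the variance would be about 1/(Np(1 − p)). At an assumed p = 0.45 this is 1/(150 × 0.2475) = 0.027 for N = 150 and 1/(15 × 0.2475) = 0.269 for N = 15, a tenfold ratio. So the premise is right in principle.

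**2. Gaze points are not independent.** Assume a 4 s window at 30 frames/s (120 frames) and looks of 0.5 to 1.2 s. The mean look is 0.85 s, so a window holds 4/0.85, or about five, looks. Simulated variance of the empirical logit at p = 0.45 (4,000 draws per cell):

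| Valid frames | Binomial formula | Scattered loss | One surviving block |
|---|---|---|---|
| 120 | 0.03 | 2.5 | 2.5 |
| 30 | 0.13 | 2.0 | 8.9 |
| 5 | 0.81 | 1.7 | 5.3 |

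The variance is far above the binomial value and does not follow 1/N. Under scattered loss it even falls. Raw N is therefore a poor guide to information, and how poor depends on the loss pattern.

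**3. What ideal weights could gain.** With one value per child and condition, the condition test is a paired difference with variance V = 2τ² + Σ 1/(n_eff·p(1 − p)). The sum runs over the two conditions, τ is the extra within-child SD on the logit scale, and n_eff is the number of valid points divided by a design effect for autocorrelation. The efficiency of equal weights relative to optimal weights is the harmonic mean of V over its arithmetic mean.

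Assumptions: 100 points in a full record, p = 0.45, design effect 1, 10 or 20, τ = 0, 0.5 or 1.0, two-sided alpha 0.05, unweighted power set to 80%.

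| Track loss (5th-95th percentile of valid points) | Relative efficiency, unweighted | Power, optimal weights | Power, raw valid-point weights |
|---|---|---|---|
| Mild (57-96) | 0.98-1.00 | 80-81% | 80-81% |
| Moderate (30-95) | 0.90-1.00 | 80-84% | 78-84% |
| Severe (7-99) | 0.55-0.98 | 81-96% | 73-96% |

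The 0.55 and the 96% need severe loss, independent points and τ = 0 together. The 73% arises with severe loss, independent points and τ = 1.0: the noncentrality is 1.96 + 0.84 = 2.80, multiplied by √0.84 it is 2.57, and Φ(2.57 − 1.96) = 0.73.

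**4. Simulated empirical logits.** 60 children, 100 points for a full record, autocorrelated gaze, 600 runs per cell. Monte Carlo error is about 2 points for power and 1 point for type I error.

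| Loss, τ | Power: unweighted | Power: valid-point weights | Power: empirical-logit variance weights |
|---|---|---|---|
| Mild, 0 | 0.54 | 0.55 | 0.29 |
| Moderate, 0 | 0.50 | 0.51 | 0.30 |
| Severe, 0 | 0.45 | 0.48 | 0.31 |
| Severe, 0.8 | 0.68 | 0.70 | 0.38 |

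Across all settings, including independent gaze, unweighted type I error was 0.04 to 0.07. Under severe loss it was 0.05 to 0.08 with valid-point weights and reached 0.10 with variance weights. Part of the small power gain with valid-point weights under severe loss therefore goes with a looser test.

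**5. The N-dependent scores.** Weights change no score. A child at 100% still scores 5.71, 4.11 or 2.40, and valid-point weights give the most influence to the 5.71. That feature belongs to the transform.

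**The case for a change.** The strongest case for a change is that a model described without weights would normally be fitted without them, and that young children filmed by webcam may well have substantial track loss. Under some assumptions the gain from valid-point weights is material. With 60 children, looks of 0.5 to 1.2 s and four trials per condition, simulated power rose from 63% to 68% at 40% loss, and in one set of runs from 64% to 80%. The large losses in the last column of the second simulation table come from variance weights, not valid-point weights. A minimum-data rule would also guard against near-empty records.

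Part of this stands. The page is silent on weighting and on minimum data, and some gain is possible when loss is heavy. But the larger gains need several trials per condition, which the document does not state, together with heavy loss. With one trial per condition, other simulations put the effect of valid-point weights at about −2 to +6 points, depending on loss pattern and within-child variation. Weighting also moves the average towards attentive children. If attention is related to learning or diagnosis, that changes the quantity estimated.

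The worry about group and interaction was not simulated. For the group contrast, variation between children adds to each child's variance, so unequal gaze error is a smaller share of the total. A group difference in track loss would matter more for the common-variance assumption, but the document gives no evidence for or against one.

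**Conclusion.** No change to the plan follows. The unequal denominators are real, but the unweighted condition test keeps close to its nominal error rate, so the issue is efficiency and not validity. The efficiency at stake runs from almost nil with mild loss to about 4 points of power with moderate loss. It is large only when loss is severe and other within-child variation is small. Raw valid-point weights are not a dependable improvement: between 73% and 96% power where the unweighted test has 80%, with type I error up to 0.08 under severe loss. Competent statisticians would differ on whether to use them.

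The remaining points are reporting detail that analysts can supply without altering the primary model: whether weights were used, how many valid points there were by group and condition, and whether results hold with a minimum of valid data or a model allowing for extra-binomial variance.

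This rests on assumed values for sample size, window, sampling rate, look length, track loss, within-child variation and alpha, because the document gives none of them. It rests on simulations of the condition effect only; group and interaction tests were not simulated.
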